4.9 INTERIM ANALYSES

4.9.1 Dose selection safety review

The dose selection safety review was performed when the first 150 participants from Stage 1 have completed 1 month of treatment (or have prematurely discontinued).

The dose selection safety review was performed by the DMC. An unblinded safety report was prepared by the external independent DMC statistician and was reviewed by the DMC. Safety data included AEs (including SAEs and AEs leading to permanent intervention discontinuation), clinical laboratory evaluation, ECG, physical and ophthalmological examination, and BDI-II data.

Based on this safety review, the DMC selected the venglustat 15mg dose for Stage 2. The venglustat 15 mg dose was the highest dose determined to be safe and well tolerated.

4.9.2 Interim futility analysis

An interim analysis for futility was performed when all participants from Stage 1 have completed the first 9 months of treatment and approximately 30% have completed 18 months of treatment with TKV available (or have prematurely discontinued).

The interim analysis was performed by the external independent statistician and was reviewed under the supervision of the DMC. The interim analysis primarily focused on the primary endpoint in Stage 1 (annualized rate of change in TKV) and stopping rules were based on this primary endpoint. Data monitoring committee also reviewed secondary efficacy endpoint (annualized rate of change in eGFR) and safety data (AEs, laboratory data, vital signs) available at the time of the interim analysis.

As per protocol, futility may be declared if the one-sided p-value of the primary endpoint at the interim analysis is >0.30. The one-sided p-value is determined from the Multiple Comparison Procedure described in Section 4.3.1.2. Based on simulations, it is expected that futility may be declared if the relative reduction versus placebo in TKV growth rate estimated at the interim analysis is approximately less than 15%. Probability to declare futility under different scenarios is presented in Section 5.6.1.

Of note, the futility rule is non-binding and provided as a guideline for the DMC but should not be considered as a strict stopping rule. In case the one-sided p-value observed at the interim analysis

is close to the pre-specified threshold, the DMC reviews the totality of data available at the time of interim analysis, including safety data (AEs, laboratory data, vital signs), and based on these data, may decide to overrule the futility rule.

If the DMC recommends continuing the study, then the Sponsor is informed of the recommendation and have no access to any unblinded results.

If the DMC recommends stopping the study for futility, then unblinded results are made available to a limited number of Sponsor's senior management team. This limited team makes the final decision to stop or continue the study. To prevent internal exposure to unblinded interim data and informal or formal discussions that can present a substantial risk to the integrity of the trial and the Sponsor's ability to manage the trial without bias, only a small designated sub team of the Sponsor is unblinded, as described in DMC charter. This Sponsor's sub team is not involved in the direct conduct of the remainder of the study and any conduct of external committees related to the study to protect the overall integrity of the study.

In order to protect the global type one error in case the decision is taken to overrule the futility rule, non-binding futility rules are used for determination of alpha.

Based on the futility analysis reviewed by DMC on the 14 May 2021, the DMC recommended to stop the analysis for futility. The Sponsor's senior management team followed this recommendation and decided to discontinue the study.

4.9.3 Two-steps analysis

Not applicable.

5 SUPPORTING DOCUMENTATION

5.1 APPENDIX 1 LIST OF ABBREVIATIONS

ADMA: Asymmetric dimethylarginine

ADPKD: Autosomal dominant polycystic kidney disease

AE: Adverse event

AESI: Adverse event of special interest

ALT: Alanine transaminase

BCVA: Best corrected visual acuity
BFI: Brief fatigue inventory
BPI: Brief pain inventory

CKD-EPI: Chronic kidney disease epidemiologic collaboration

CRF: electronic case report form DBP: Diastolic blood pressure ECG: Electrocardiogram

eGFR: estimated glomerular filtration rate EQ 5D-5L: EuroQol 5 dimensions 5-level FGF23: Fibroblast growth factor 23 GCS: Glucosylceramide synthase

GL-1: Glucosylceramide

GM3: Monosialodihexosylganglioside

HGLT: High level group term HLT: High level term

htTLV: height adjusted total liver volume

ICF: Inform consent form

IRT: Interactive response technology

ITT: Intent-to-treat

LLOQ: Lower limit of quantification

LLT: Lower level term

LOCSIII: Lens opacities classification system III MedDRA: Mecical dictionary for regulatory activities

mGFR: measured glomerular filtration rate MMRM: Mixed model with repeated measures

MRI: Magnetic resonance imaging

NRS: Numeric rating scale OTC: Over the counter

PCSA: Potentially clinically significant abnormality

PD: Pharmacodynamic

PGIC: Patient global impression of change PGIS: Patient global impression of severity

PK: Pharmacokinetic

PRO: Patient reported outcome

PT: Preferred term

SAE: Serious adverse event
SBP: Systolic blood pressure
SD: Standard deviation
SE: Standard error
SOC: System organ class
TE: Treatment emergent

TEAE: Treatment emergent adverse event

TKV: Total kidney volume TLV: Total liver volume

ULOQ: Upper limit of quantification

WHO-DD: World Health Organization-drug dictionary

5.2 APPENDIX 2 CHANGES TO PROTOCOL-PLANNED ANALYSES

This section summarizes major statistical changes in the protocol amendment(s).

Table 9 - Major statistical changes in protocol amendment(s)

Amendment Number	Approval Changes Rationale Date		Rationale
01	19 April 2018	Clarification on the timing of evaluation of the secondary and exploratory endpoints	To clarify
		Clarification of possible course of action with regard of study dose in ongoing participants in Stage 1 after DMC review of safety data and dose selection for Stage 2	To clarify
		Clarification on mGFR stusudy	To clarify that mGFR substudy is optional for eligible participants
02	25 May 2018	Addition of stratification of participants by region	To achieve balance between the treatmen arms across the different regions
		Removal of exploratory objective of the study on mGFR sub-study	
		Addition of exploratory objectives of the study on effect of GZ/SAR402671 on type, frequency and dosage of analgesic/over the counter (OTC) pain medication administration	To explore the effect of GZ/SAR402671 or type, frequency and dosage of analgesic/over the counter pain medication administration
		Update of items of the Daily symptoms of autosomal dominant polycystic kidney disease diary to regroup pain and nocturia items of the diary and to add an additional item that will direct to the medication entry log	
		Addition of secondary analysis on TKV assessed from 1 month to 18 months, excluding baseline	To describe secondary analysis that will explore a potential acute hemodynamic effect using TKV data assessed from 1 month to 18 months
03	01 October 2018	Description of objective of mGFR substudy	To explore the effect of GZ/SAR402671 or measured GFR (mGFR) substudy
		Added exploratory endpoint of Annualized rate of change in mGFR from baseline to 24 months in participants within Stage 2 substudy	

Amendment Approval Number Date				Changes	Rationale
04	14 Aug 2019	Increase of the sample size for the Inclusion in Stage 2 of the study of 80 participants with a screening eGFR between 30 and 44.9 mL/min/1.73 m ² Addition of exploratory endpoint of Annualized rate of change in eGFR (CKD-EPI equation) from baseline to 24 months in participants with a screening eGFR between 30 and 44.9 mL/min/1.73 m ² added	To explore the effect of venglustat on eGFR (CKD-EPI equation) from baseline to 24 months in participants with a screening eGFR between 30 and 44.9 mL/min/1.73 m ²		
		Addition of statistical consideration related to probability of detecting a treatment effect in an additional 80 participants with screening eGFR between 30 and 44.9 mL/min/1.73 m ²			
		Addition of clarification to the definition of the combined Stage 1 and Stage 2 Safety population will be defined as all randomized participants with eGFR between 45 and 89.9 mL/min/1.73 m² at screening and participants from Stage 2 with an eGFR between 30 and 44.9 mL/min/1.73 m² at screening will be analyzed separately			
		Described secondary analysis including participants from Stage 2 with eGFR between 30 and 44.9 mL/min/1.73 m² at screening			
		Clarification of inclusion criteria: between the ages of 18 to and 50 years (both inclusive) at screening for participants in Stage 1	To clarify and add participants with screening eGFR between 30 and 44.9 mL/min/1.73 m ²		
	for participants in Stage 2 v eGFR between 45 an	between 18 and 50 years (inclusive) for participants in Stage 2 with an eGFR between 45 and 89.9 mL/min/1.73 m² during the screening period*			
		between 18 and 55 years (inclusive) for participants in Stage 2 with an eGFR between 30 and 44.9 mL/min/1.73 m² during the screening period			
		Systolic BP >160 mmHg* at run in and baseline visits. *mean value of three or five systolic BP measurements	To clarify calculation of SBP		

Amendment Approval Number Date		Changes	Rationale
		Clarification of the timing of the secondary analysis of TKV. TKV assessed more than 30 days instead of 4 weeks after the last IMP administration will be excluded from the analysis	To clarify
		Clarification of the residual treatment period defined as the time from the day after the last IMP administration, plus 30 days (instead of 4 weeks)	To clarify
		Clarification that the baseline value is defined generally as the last available value before first IMP administration	To clarify
		Clarification that opacities present at baseline/previous visit, changes in LOCSIII score of ≥0.5 for nuclear opalescence, ≥0.8 for cortical opacification, or ≥0.5 for posterior subcapsular opacification compared with baseline or previous assessment will be considered as a worsening	To specify threshold for minimal significant change in LOCSIII score that will be considered as a worsening of lens opacity
05	17 Aug 2020	Updated the hierarchy of the secondary and exploratory endpoints: 1. pain and fatigue are moved from exploratory to secondary endpoints	Data from venglustat clinical studies do not suggest that venglustat causes urinary frequency or nocturia. For this reason, the change in nocturia was moved from secondary to exploratory endpoints.
		nocturia and urine osmolality (Stage 2) are moved from secondary to exploratory endpoints	Pain and fatigue were moved from exploratory to secondary endpoints as they are fit in ADPKD as the concepts for which a positive effect can be shown.
		PRO population deleted	PRO analysis will be performed on ITT population
		Removal of sentence "Time of baseline TKV will be set to 0."	Time of baseline TKV will be calculated as relative time since randomization date.
		Change in definition of on-treatment period and treatment-emergent period	Clarification
		Presentation of statistical tables by SOC and PT	Clarification
		Statistical analysis of liver test data	Clarification
		Statistical analysis of PRO data using MMRM	Clarification
		Primary analysis of Stage 1 will include data available at the cut-off date, including data reported up to Month 24, if any	Clarification

Amendment Number	Approval Date	Changes	Rationale
06 16 Dec 2020		Added clarification that GFR will be measured with iohexol in patients with the screening eGFR between 45 and 89.9 mL/min/1.73 m ²	Clarification
		Added inclusion criterion related to the screening eGFR value in patients eligible for the mGFR substudy	Clarification
07	19 Apr 2021	Exploratory objectives and corresponding endpoints were updated to consider all-cause hospitalization	Clarification
		Added clarification that for patients to be screened for the long-term extension study after Month 24 (Visit 12) and prior to Month 13 (Visit 13), the last in Study EFC15392 should coincide with the first visit in the long-term extension study	Clarification
		For patients enrolled or screened for the long-term extension study prior to 30 days after the last dose of IMP, all SAEs, AEs, and AEs of special interest (AESIs) will be collected up to the last visit in Study EFC15392, which will coincide with the first visit in the long-term extension study	Clarification
		Added information that samples for exploratory biomarkers analysis collected in Stage 2 of the study will be analyzed only if results of this analysis during Stage 1 are considered as useful for further investigation. Removed collection of serum/plasma and urine biomarker samples at Visit 4 (Month 1) in Stage 2	Optimization, clarification
		Numbers of patients and samples for pharmacodynamics and exploratory biomarkers were updated.	Correction
		The definition of residual treatment period was updated.	Clarification
		Changes in previous amendment 06 that were specific to the USA, the Netherlands, and Canada will be now applicable for all the countries for this	To extend the conduct of the Measured Glomerular Filtration Rate (mGFR) substudy to all countries participating in the EFC15392 study.
		amendment 07, with the exception of the additional inclusion criteria asking for an eGFR between 45 and 89.9 mL/min/1.73 m² that is no longer applicable for participants enrolling to the sub-study.	Correction (all patients, patients with any screening eGFR value, in Stage 2 can be potentially eligible for mGFR study).

5.3 APPENDIX 3 DEMOGRAPHICS AND BASELINE CHARACTERISTICS, PRIOR OR CONCOMITANT MEDICATIONS

The following demographics and baseline characteristics, medical and surgical history and disease characteristics will be summarized using descriptive statistics in the randomized population.

Demographic and baseline characteristics

- Gender (Male, Female)
- Age in years (quantitative and categorical variable: <40, and ≥40 years),
- Race (White, Black or African American, Asian, American Indian or Alaska Native, Native Hawaiian or other Pacific Island, other)
- Ethnicity (Hispanic, non-Hispanic)
- Weight in kilograms (quantitative and categorical variable: <50, 50 to <100, ≥100)
- Body mass index (BMI) in kg/m² (quantitative and categorical variable: $<30, \ge 30$)

Randomization strata

The randomization strata of predicted ADPKD progression rate (1C versus 1D versus 1E) according to Mayo Imaging Classification and region (North America, Europe, China, Japan, Republic of Korea, Rest of the World) as recording in IRT as well as actual strata (see Section 5.4).

Disease characteristics

eGFR at screening and at baseline (quantitative variable and qualitative variable: <30,30 to <45, 45 to <60, 60 to <75, 75 to <90, >=90) (see Section 5.4).

ADPKD gene mutation

The listing of participants with a genetic testing ever performed will be presented including the affected gene, the DNA sequence change and the AA change.

Medical or surgical history

Medical (or surgical) history includes previous relevant medical and surgery history collected at baseline. Medical and surgical history will be coded to a LLT, PT, HLT, HLGT, and associated primary SOC using the MedDRA version currently in effect at Sanofi at the time of database lock.

Medical/surgical history will be summarized in each treatment arm by primary SOC and PT. Events will be sorted by SOC internationally agreed order and decreasing frequency of PT based on the incidence in the overall treatment arm.

Alcohol habits at baseline

Alcohol habits include:

- Frequency of alcoholic drinks in the last 12 months (Never/Occasional/At least monthly/At least weekly/At least daily)
- Number of standard drinks (1 or 2/Greater than 2, where standard drink means 1 pint/bottle of beer, 1 glass of wine, 1 shot of hard liquor...) per day when drinking alcohol

Baseline safety and efficacy parameters (apart from those listed above) will be presented along with the safety and efficacy summaries.

Prior or concomitant medications

All medications will be coded using the World Health Organization-Drug Dictionary (WHO-DD) using the version currently in effect at Sanofi at the time of database lock:

- Prior medications are those the participant used prior to first IMP intake. Prior medications can be discontinued before first administration or can be ongoing during treatment period.
- Concomitant medications are any medications received by the participant concomitantly to the IMP during the on-treatment period.
- Post-treatment medications are those the participant took in the period running from the end of the concomitant medications period up to the end of the study.
- A given medication can be classified as a prior medication and/or as a concomitant medication and/or as post-treatment medication. If it cannot be determined whether a given medication was taken prior or concomitantly or post, it will be considered as prior, concomitant, and post-treatment medication.

The prior and concomitant medications will be summarized for the randomized and exposed population, by anatomic and therapeutic level. The summaries for prior medications will be sorted by decreasing frequency of anatomic category (ATC) based on the overall incidence across study intervention group. The summaries for concomitant medications will be sorted by decreasing frequency of ATC based on the incidence the venglustat 15 mg group. In case of equal frequency, alphabetical order will be used.

Participants will be counted once in each ATC category (anatomic or therapeutic) linked to the medication.

In addition, any concomitant pain medication will be summarized.

5.4 APPENDIX 4 DATA HANDLING CONVENTIONS

General conventions

The following formulas will be used for computation of parameters.

Demographic formulas

• BMI =
$$\frac{\text{weight(kg)}}{\text{height(m)}^2}$$

Total kidney volume and total liver volume using MRI

All TKVs are evaluated by 2 independent reviewers and adjudicated in case of inconsistency (percentage difference $\geq 6\%$).

At each visit, the TKV selected by the adjudication, if any, will be used for analyses. Else the mean of the TKV provided by the 2 independent reviewers will be considered.

TLVs were evaluated by 2 independent reviewers at the start of the study for few participants, then upon team agreement evaluated by only one reviewer. At each visit, the mean of the TLV provided by the 2 independent reviewers, if any, will be considered for analysis.

Mayo imaging classification strata based on height-adjusted TKV (HtTKV in mL/m) relative to age

Actual Mayo imaging classification strata is based on participant's height adjusted TKV at screening (using TKV assessed by the screening radiologist) and age using the TKV growth rate per year r defined as (9):

$$r = 10**((log_{10}(htTKV) - log_{10}(150)) / age) - 1$$

Then the Mayo imaging classification will be defined as follows:

Table 10 - Mayo imaging classification

r	Mayo Imaging classification
<1.5%	1A
1.5% to <3.0%	1B
3.0% to <4.5%	1C
4.5% to < 6.0%	1D
≥6.0%	1E

eGFR at screening

The screening eGFR is defined as the eGFR value that was selected to enroll the participant in the study:

- If eGFR at Visit 1 was between 45 and 89.9 mL/min/1.73 m² (or between 30 and 89.9 mL/min/1.73 m² for Stage 2), then the value at Visit 1 is considered as the screening value
- Else, if an additional eGFR measurement was done between Visit 1 and Visit 2, then this additional value is considered as the screening value
- Else, the eGFR at Visit 2 is considered as the screening value

Table 11 - eGFR values example

Subject	V1	Additional (between V1 and V2)	V2
1	87	ND	91
2	92	ND	85
3	95	86	93
4	92	95	88

eGFR at baseline

Baseline eGFR is defined for each participant as the average of eGFR values assessed prior or equal to 1st IMP or prior or equal to randomization for randomized and not exposed participants.

Analysis windows for time points

For efficacy and patient reported outcome endpoints, D1 will be defined as the day of randomization. For safety endpoints, D1 will be defined as the day of first IMP intake.

For endpoints not collected at each visit (including TKV, TLV, weight, height, ECG, complete physical examination, neurological examination and daily diaries), analysis by time points will be summarized using the protocol planned visits.

For endpoints collected at almost each visit, the following analysis windows will decide how the scheduled and/or unscheduled visits will be used in the by-visit analyses of efficacy data (eGFR, urine osmolality), laboratory safety data (except urinalysis parameters), vital signs, (except weight and height), ophthalmological examination, patient reported outcome variables as well as PK variables. Only central assessments will be taken into account. For each parameter, only analysis time windows corresponding to a protocol planned visit for that parameter are applicable.

A measurement (scheduled or unscheduled) will be used if it is available and measurement date is within the analysis window.

After applying these time windows, if multiple assessments are associated to the same time point, the value collected at the scheduled visit will be used, if any. Otherwise the closest from the targeted study day will be used. If the difference is a tie, the value after the targeted study day will

be used. For all endpoints except PK, if multiple valid values exist within a same day, then the first value of the day will be selected.

If there is no measurement for a given parameter in an analysis window, data will be considered missing for the corresponding visit.

Table 12 - Analyses window definition

Time point	Targeted study day	Analysis window in study days
Month 1	D30	D2 to D60
Month 3	D90	D61 to D135
Month 6	D180	D136 to D225
Month 9	D270	D226 to D315
Month 12	D360	D316 to D405
Month 15	D450	D406 to D495
Month 18	D540	D496 to D585
Month 21	D630	D586 to D675
Month 24	D720	D676 to D765

Table 13 - Analyses window definition for PK analyses - Stage 1

Time point	Target study day	Analysis window	
Day 1/Post-dose	Day 1/3 hours Post-dose	2h00 to 4h00 after Day 1 dose	
Month 1/Pre-dose	D30/Pre-dose	Before Month 1/Day 30 dose	
Month 1/Post dose	D30/3 hours post dose	2h00 to 4h00 after Month 1/Day 30	
Months 6/Pre-dose D180/Pre-dose I		Before Months 6/Day 180 dose	
Months 18/Pre-dose	D540/Pre-dose	Before Months 1/Day 540 dose	

Table 14 - Analyses window definition for PK analyses - Stage 2

Time point Target study day		Analysis window
Month 1/Pre-dose	D30/Pre-dose	Before Month 1/Day 30 dose
Month 1/Post dose	D30/3 hours post dose	2h00 to 4h00 after Month 1/Day 30
Months 24/Pre-dose	D720/Pre-dose	Before Months 24/Day 720 dose

Unscheduled visits

Unscheduled visit measurements will be used for computation of baseline, the last on-treatment value and worst on-treatment value. For parameters summarized according to analysis time windows, unscheduled visit measurements may also be used to provide a measurement for a timepoint.

For efficacy analyses based on annualized rate of change, all assessments at planned visits and unscheduled visits will be taken into account.

For laboratory data, vital signs and ECG analysis unscheduled visit measurements will be used to provide the analysis according to the PCSA and the shift summaries for safety.

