### **6.5.2 Rationale for study design and control groups**

This study is designed to demonstrate the efficacy by slowing the progression of kidney volume and concomitantly evaluate the effect on worsening renal function, patient reported outcome (PRO) and liver volume in patients with ADPKD. Due to the high variability of eGFR, the primary endpoint of Stage 1 is TKV growth rate while the primary endpoint in Stage 2 is the slope

of eGFR. Safety, tolerability, PK, and PD effects of venglustat are supported by Phase 1 and Phase 2 studies and animal toxicology data in rodents up to 26 weeks and dogs up to 39 weeks. In vitro and in vivo genotoxicity studies have been conducted and are negative. Carcinogenicity studies have not yet been conducted.

A prognostic enrichment approach is used to select patients for primary analysis population who will be at risk for rapid progression of disease based on those aged between 18 to 50 years, CKD Stages 2-3A, and Mayo Imaging Classification of ADPKD Class 1C-E. This enrichment allows the detection of treatment benefit on both TKV and GFR in the same population thus circumventing the need for performing separate trials in "early" and "late" ADPKD patients.

Patients with eGFR  $<45$  mL/min/1.73 m^2 aged 18 to 55 years old recruited in Stage 2 of the study will be not included in primary analysis population but the data from these patients will be analyzed separately.

Patients with CKD Stage 3b (eGFR 30 - 45 mL/min/1.73 m^2) aged 18 to 55 years old will be recruited in Stage 2 of the study to permit gathering information on venglustat in this severely affected patient population. However, this patient population will not be included in the Stage 2 primary analysis but will be analyzed separately. The rationale for including these patients in the study is to obtain further information on venglustat exposure, safety and efficacy in patients with lower renal function.

Based on the mode of action of venglustat the benefit of disease modification is expected to decrease whereas the exposures of venglustat increase with declining renal function. For this reason, CKD Stage 4 patients (eGFR  $<30$  mL/min/1.73 m^2) will not be included into the study.

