### 7.1 INCLUSION CRITERIA

I 01. Male or female adult with ADPKD with an age at the time the consent is signed:

- a) between 18 and 50 years (inclusive) for patients in Stage 1
- b) between 18 and 50 years (inclusive) for patients in Stage 2 with an eGFR between 45 and 89.9 mL/min/1.73 m^2 during the screening period\*
- c) between 18 and 55 years (inclusive) for patients in Stage 2 with an eGFR between 30 and 44.9 mL/min/1.73 m^2 during the screening period\*

Diagnosis of ADPKD in patients with a family history, will be based on unified Pei criteria (12). In the absence of a family history, the diagnosis will be based on the presence of renal cysts bilaterally, totaling at least 20, in the absence of findings suggestive of other cystic renal diseases.

I 02. Mayo Imaging Classification of ADPKD Class 1C, 1D, or 1E\*\* (3).

\*\*TKV volume must be confirmed by a central reader prior to Visit 3.

I 03. Estimated glomerular filtration rate between 45 and 89.9 mL/min/1.73 m^2 during the screening period\* (Chronic Kidney Disease Epidemiology Collaboration [CKD-EPI] equation) for Stage 1.

Estimated glomerular filtration rate between 30 and 89.9 mL/min/1.73 m^2 during the screening period\* (CKD-EPI equation) for Stage 2.

\*Eligibility will be confirmed by the eGFR value from one of the two first pre-randomization eGFR measurements (Visit 1 or Visit 2 measurements or Visit 1 and an additional measurement performed at the Investigator's discretion between Visit 1 and Visit 2).

I 04. Stable treatment regimen of antihypertensive therapy for at least 30 days prior to the screening visit for hypertensive patient.

I 05. Able to read, comprehend, and respond to the study questionnaires.

- I 06. Patient has given voluntary written informed consent before performance of any study related procedures not part of standard medical care.
- I 07. Patient does not have access to tolvaptan at the time of study start or tolvaptan is not indicated for treatment of patient according to treating physician (patient does not meet recommended criteria for treatment, refuses to initiate or does not tolerate treatment with tolvaptan).
- I 08. The patient, if female of childbearing potential, must have a negative blood pregnancy test ( $\beta$ -human chorionic gonadotropin [ $\beta$ -hCG]) at the screening visit and a negative urine pregnancy test at the baseline visit.

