3 ANALYSIS POPULATIONS

The following populations for analyses are defined:

Table 4 - Populations for analyses

Population	Description
Screened	All participants who signed the Informed Consent Form (ICF).
Randomized	All participants from screened population who have been allocated to a randomized intervention by Interactive Response Technology (IRT) regardless of whether the intervention was received or not.
Exposed	All screened participants who took at least 1 dose of study intervention.
Population without trial impact (disruption) due to COVID-19	All randomized participants without any critical or major deviation related to COVID19 and who did not permanently discontinue treatment due to COVID19 and who did not permanently discontinue study due to COVID19
Stage 1 Intent-to-treat (ITT)	All participants randomized in Stage 1.
	Participants will be analyzed according to the intervention allocated by randomization (venglustat 15 mg, venglustat 8 mg or placebo).
Stage 1 Pharmacokinetic (PK)	All participants randomized in Stage 1 who took at least 1 dose of study intervention and who have at least one post-baseline PK assessment. Participants will be analyzed according to the intervention they actually received.
Stage 1 Pharmacodynamic (PD)	All participants randomized in Stage 1 who took at least 1 dose of study intervention and who have at least one post-baseline PD assessment. Participants will be analyzed according to the intervention they actually received.
Combined Stage 1 and Stage 2 ITT	All participants with an eGFR between 45 and 89.9 mL/min/1.73 m ² at screening who are randomized in Stage 1 or Stage 2.
	Participants will be analyzed according to the intervention allocated by randomization (venglustat 15 mg, venglustat 8 mg or placebo).
Secondary Stage 2 ITT	All participants with an eGFR between 30 and 44.9 mL/min/1.73 m ² at screening who are randomized in Stage 2. Participants will be analyzed according to the intervention allocated by randomization (venglustat 15 mg or placebo).
Extended Combined Stage 1 and Stage 2 Safety	All participants with an eGFR between 30 and 89.9 mL/min/1.73 m ² at screening who are randomized in Stage 1 or Stage 2 and who took at least 1 dose of study intervention. Participants will be analyzed according to the intervention they actually received.

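### The SAP's order-based rule for screening eGFR could place Stage 2 participants aged 51-55 in the primary eGFR population, against its own definition of that value

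*SAP*

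**What the plan says.** **Eligibility (Protocol 7.1).** I 01 b sets the first Stage 2 age band: "between 18 and 50 years (inclusive) for patients in Stage 2 with an eGFR between 45 and 89.9". I 01 c sets the second: "between 18 and 55 years (inclusive) for patients in Stage 2 with an eGFR between 30 and 44.9". Ages 51-55 therefore have one route into the study. The footnote on timing reads: "Eligibility will be confirmed by the eGFR value from one of the two first pre-randomization eGFR measurements". It names Visit 1 and Visit 2, or Visit 1 and an additional measurement between the two.

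**Screening value (SAP 5.4, eGFR at screening).** The lead-in states: "The screening eGFR is defined as the eGFR value that was selected to enroll the participant in the study". Three ordered bullets follow:
- Visit 1 is used if it lies in 45-89.9 (30-89.9 in Stage 2): "then the value at Visit 1 is considered as the screening value".
- Otherwise an additional measurement is used, if one was taken.
- Otherwise Visit 2 is used.

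No bullet mentions age, and the second and third do not check the range.

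**Populations (SAP 3, Table 4).** The Combined Stage 1 and Stage 2 ITT is everyone with eGFR 45-89.9 "at screening who are randomized in Stage 1 or Stage 2". The Secondary Stage 2 ITT is Stage 2 participants with 30-44.9. The Stage 2 PK and Combined PD populations also use 45-89.9. None of these definitions has an age criterion.

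**Intended primary population (Protocol 6.5.2).** It is described as those "aged between 18 to 50 years, CKD Stages 2-3A, and Mayo Imaging Classification of ADPKD Class 1C-E". The same section justifies combining the stages partly on the ground that entry criteria for the primary analysis population are identical in both.

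**The concern.** For a participant aged 51-55, the value that qualified him or her must lie in 30-44.9. If that value was not Visit 1, and Visit 1 was 45 or more, the lead-in and the first bullet give different answers, and the derived value decides the cohort. Randomization is stratified by Mayo class and region, not by eGFR cohort, so no stratum label corrects the assignment.

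Two things are at stake. The primary eGFR population could take in participants older than the enrichment design intends. The planned cohort of 80 could lose some of the participants for whom it was opened to age 55. Both populations are still used in SAP version 2: the Combined ITT for the eGFR mixed model (4.3.2.2) and the Secondary Stage 2 ITT for the descriptive eGFR summary (4.3.2.4).

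**Working it through.** The documents state no figure to reproduce. The check applies the bullets to cases and then illustrates how often they could go wrong.

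**1. Stage 2, age 53, bullets applied literally**

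| Visit 1 | Additional | Visit 2 | Qualifying value under I 01 c | Value from SAP bullets | Population by Table 4 |
|---|---|---|---|---|---|
| 47 | none | 43 | 43 | 47 | Combined ITT |
| 47 | 43 | 46 | 43 | 47 | Combined ITT |
| 43 | none | 46 | 43 | 43 | Secondary Stage 2 ITT |
| 92 | none | 43 | 43 | 43 | Secondary Stage 2 ITT |

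The rule fails when Visit 1 is in 45-89.9 and the qualifying value is a later one below 45.

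**2. Table 11 subjects, bullets applied literally**

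Subjects 1 to 4 receive 87, 85, 86 and 95. All the listed values are 85 or above, so the table never tests the boundary at 45. Subject 4 (Visit 1 = 92, additional = 95, Visit 2 = 88) receives 95, which is outside every eligible range. A participant with 95 as screening value would also fall outside the 45-89.9 definition of the Combined ITT. Whether 88 could have qualified this subject depends on whether Visit 2 still counts once an additional measurement exists, and the Protocol 7.1 footnote can be read either way. On neither reading is 95 the enrolling value.

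**3. Illustration of frequency**

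Assumptions, none of them document figures except one:
- True eGFR of candidates aged 51-55 is normal, with mean 38, 41 or 45 and SD 6 or 10.
- Visit 1 and Visit 2 add independent normal error with SD 2, 3, 4 or 6.34. The last is the residual SD in the sample size section of both documents.
- Every candidate reaches Visit 2, and no additional measurement is taken.

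Eligible: at least one of the two values is in 30-44.9. Moved: Visit 1 in 45-89.9 and Visit 2 in 30-44.9. Share = moved / eligible, with 2 million simulated candidates per setting.

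| Mean, SD of true eGFR | error SD 2 | error SD 3 | error SD 4 | error SD 6.34 |
|---|---|---|---|---|
| 38, 6 | 4.6% | 6.9% | 9.2% | 13.6% |
| 38, 10 | 5.8% | 8.2% | 10.6% | 14.7% |
| 41, 6 | 7.6% | 10.8% | 13.7% | 18.5% |
| 41, 10 | 7.1% | 10.1% | 12.7% | 17.3% |
| 45, 6 | 12.7% | 17.1% | 20.6% | 25.5% |
| 45, 10 | 9.1% | 12.8% | 15.8% | 21.1% |

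With true eGFR uniform on 30-45 or 30-60 and error SD 2, 4 or 6.34, the share is 3.9% to 19.3%.

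**4. From shares to patients**

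Suppose 20 to 40 of the planned 80 are aged 51-55 (assumed).
- Low end: 0.046 × 20 = 0.9 patients.
- High end: 0.255 × 40 = 10.2 patients.
- The high end is 10.2 / 560 = 1.8% of the planned primary population (240 + 320 = 560), and 10.2 / 80 = 12.8% of the planned cohort.

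**The case against.** **The lead-in already gives the right answer.** Read alone, it does: for the 53-year-old it returns 43. That makes this a conflict inside one paragraph and not a settled wrong rule. But the bullets are the operational part, and a programmer would code those.

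**It may never occur.** Protocol 10.1.1.2 has eligibility confirmed from screening-visit results before run-in capsules are given, so a site might screen-fail anyone over 50 with Visit 1 of 45 or more. If all sites did so, the count is zero. Protocol 7.1 does not require it, and lets a later value qualify the patient. This objection stands as a limit on frequency: the simulated shares assume that nobody is screen-failed and so lean high. The 6.34 is also a residual SD from a slope model in historical studies, not repeatability over about two weeks.

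**Little now depends on it.** SAP version 2 follows the decision to stop for futility. Safety is pooled over 30-89.9, combined TKV is not analysed, and the model of treatment effect by baseline eGFR has become a descriptive summary. What remains is the combined eGFR slope model, one descriptive table, and the PK and PD summaries. The totals of 560 and 80 are planned numbers. This stands.

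**Stronger readings.** A reader might infer that participants aged 51-55 are known to be in the primary population, or that the eGFR comparison is biased. The documents support neither. They give no count of such participants or of discordant screening values. Misplacement depends only on values taken before randomization, so it cannot depend on the assigned arm.

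**Conclusion.** The point holds as a conflict in the derivation. For a Stage 2 participant aged 51-55 with Visit 1 of 45 or more who qualified on a later value of 30-44.9, the first bullet contradicts the SAP's own lead-in and the 18-50 age range of the primary population. Such a participant would enter the Combined ITT (and, where otherwise eligible, the Stage 2 PK and Combined PD populations) and leave the Secondary Stage 2 ITT. The second bullet shares the flaw, as Table 11 subject 4 shows.

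That textual conflict needs no assumption. Its frequency does: roughly 5% to 25% of eligible 51-55-year-olds under the normal settings above, most likely a few patients and possibly none. Little bias in the slope difference is expected. The consequence is for the definition of the populations and, proportionally more, for the small 30-44.9 cohort. It should be corrected, but it does not threaten the primary result.

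**What to change.** Add to SAP 5.4: the screening eGFR is the first protocol-permitted value, in the order Visit 1, additional (if done), Visit 2, that meets the eGFR range for the participant's stage and age at consent under I 01 and I 03. For ages 51-55 in Stage 2 that range is 30-44.9. State that this prevails over the order of the bullets, and say whether Visit 2 is a permitted value once an additional measurement has been taken. Add one Table 11 example near 45 for a participant over 50, and show the assigned value for subject 4.

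With this rule, no participant aged 51-55 who was enrolled on a value of 30-44.9 enters the Combined ITT. The cost is a sentence or two and one derivation line. No new data are needed, and the loss from the primary population is at most the few participants who do not belong there.
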